### **8.2.1 Additional Statistical Considerations**

The objective of the statistical analyses is to assess the efficacy and safety of upadacitinib for the treatment of subjects with moderate to severe PN who are candidates for systemic therapy. The Primary Analysis for all efficacy endpoints will be conducted after all continuing subjects have completed the study activities up to Week 16. The Intent-to-Treat (ITT) Population consists of all randomized subjects and will be used for the efficacy analyses. A Per-Protocol Population may be defined if deemed necessary to exclude subjects with major protocol violations. The criteria to define the Per-protocol Population will be detailed in the SAP. Subjects to be excluded from the Per-Protocol Population will be finalized before week 16. The Per-Protocol Population, if defined, will be used to analyze the primary efficacy endpoint.

The Safety Population consists of all randomized subjects who received at least 1 dose of study drug. An All Upadacitinib Treated Population consists of all subjects who received at least one dose of upadacitinib in the study. This population will be used to provide a comprehensive summary of safety.

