Study Endpoints	Primary Endpoint: Proportion of participants with improvement (reduction) in worst-itch numeric rating scale (WI-NRS) by $\geq 4$ from baseline to Week 12. [Time Frame: Baseline to Week 12 ]WI-NRS is a patient-reported outcome (PRO) comprised of a single item rated on a scale from 0 ("No itch") to 10 ("Worst imaginable itch). Secondary Endpoints: Proportion of patients with improvement in worst-itch numeric rating scale (WI-NRS) by $\geq 4$ from baseline to Week 24 IGA PN-S 0 or 1 at weeks 12 & 24 IGA PN-A 0 or 1 at week 12 & 24 Percent improvement of PN-S & PN-A at week 12 & 24 DLQI improvement at weeks 12 & 24 Adverse Events
References	Tessa B. Mullins, Poonam Sharma, Christopher A. Riley, Sidharth Sonthalia. Prurigo Nodularis. StatPearls [Internet]. Treasure Island (FL): StatPearls Publishing; 2021 Jan. 2020 Sep 15.  Eric H Kowalski, Diana Kneiber, Manuel Valdebran, Umangi Patel, Kyle T Amber. Treatment-resistant prurigo nodularis: challenges and solutions. Clin Cosmet Investig Dermatol. 2019 Feb 28;12:163-172. doi: 10.2147/CCID.S188070. eCollection 2019.

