#### **5.5.1.3 Upadacitinib Dosage Adjustments**

Upadacitinib will be dispensed and administered as 15mg QD at baseline. For subjects who do not achieve  $\leq$  2-point reduction in itch at week 8, upadacitinib dosage will be increased to 30mg QD. The investigator may reduce the dose to 15mg QD after week 16 per investigator discretion. If an SAE or an adverse event that is thought to be related to study drug and is not alleviated by symptomatic intervention, study drug will be discontinued. Subjects who permanently discontinue study drug under this protocol should receive standard care of prurigo nodularis treatment as prescribed by their physician.

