### **5.6 Study Procedures**

This protocol will consist of a Screening Period (0-30 days), followed by open label treatment period of upadacitinib 15mg-30mg QD for 24 weeks. To date, Dupixent is the first and only medication to demonstrate positive results in prurigo nodularis at week 24 and receive regulatory approval for PN. This study will explore efficacy over a 24-week period to evaluate clinical response.

This Study will be conducted in compliance with CFR Title 21, Part 50 (Informed Consent of Human Subjects). Informed consent will be obtained from each subject in writing before participation in the Study. A signed copy of the Informed Consent Form will be provided to each subject. A provision to obtain a signed authorization to provide protected health information to the study sponsor, internal quality assurance agencies, health

insurance agencies, and other parties as specified in the Federal Health Insurance Portability and Accountability Act (HIPAA) privacy regulation will be included in the Informed Consent Document. HIPAA authorization is voluntary. However, since the use and release of health information is critical to the conduct of the study, subjects who do not provide authorization to use and disclose their health information will not be enrolled into the study. Subjects who withdraw their authorization to use and release health information during study participation will be formally discontinued from the study. The investigator may use and release at any time all the information collected prior to a subject's withdrawal of the authorization to all authorized parties to satisfy scientific, regulatory, and financial concerns.

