## **8.2 Statistics**

It is desired to enroll 25 patients.

Primary Endpoint: Proportion of participants with improvement (reduction) in worst-itch numeric rating scale (WI-NRS) by  $\geq 4$  from baseline to Week 16 [Time Frame: Baseline to Week 12] WI-NRS is a patient-reported outcome (PRO) comprised of a single item rated on a scale from 0 ("No itch") to 10 ("Worst imaginable itch").

Secondary Endpoints: Percent improvement (reduction) in worst-itch numeric rating scale (WI-NRS) by  $\geq 4$  from baseline to Week 24

IGA PN-S 0 or 1 at weeks 12 & 24

IGA PN-A 0 or 1 at week 12 & 24

Percent improvement of PN-S & PN-A at week 12 & 24

DLQI improvement at weeks 12 & 24

Adverse Events

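### Section 8.2.1 ties the Primary Analysis of all efficacy endpoints to Week 16, but half of the efficacy results are measured at Week 24 and no later analysis is described

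*Combined protocol and SAP*

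**What the plan says.** Section 8.2.1 gives the only analysis time in the document: "The Primary Analysis for all efficacy endpoints will be conducted after all continuing subjects have completed the study activities up to Week 16".

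The endpoint lists in the Synopsis and Section 8.2 place the efficacy results as follows.

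- **Primary (WI-NRS response):** the Synopsis has "from baseline to Week 12. [Time Frame: Baseline to Week 12"; Section 8.2 has "from baseline to Week 16 [Time Frame: Baseline to Week 12".
- **Secondary WI-NRS:** "from baseline to Week 24".
- **Other secondary measures:** for example "IGA PN-S 0 or 1 at weeks 12 & 24" and "DLQI improvement at weeks 12 & 24". IGA PN-A 0 or 1 and the percent improvements in PN-S and PN-A have the same two time points.

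Section 5.6 describes a screening period "followed by open label treatment period of upadacitinib 15mg-30mg QD for 24 weeks". In the Schedule of Events (Section 8.3), Week 16 is V6 and Week 24 is V8, and every subject has efficacy assessments and questionnaires at both. The efficacy paragraph after Section 8.2.1 puts all efficacy endpoints on the ITT population and does not impute missing data. Section 8.2.1 refers to a SAP only for the per-protocol criteria. It also requires per-protocol exclusions to be settled before Week 16.

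**The concern.** The timing sentence covers every efficacy endpoint, so it takes in results that will not yet exist for the subjects enrolled last. If the last subject stays in the study, that subject's Week 24 visit falls 8 weeks after the cut-off, whatever the accrual pattern.

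At stake are the Week 24 results. The title describes a 24-week study, and Section 5.6 says that efficacy is explored over 24 weeks. A Week 24 response proportion taken at the stated cut-off would describe the earlier enrolees, not the 25 subjects intended, and would not fit the commitment to analyse all efficacy endpoints on the ITT population.

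This is a separate matter from the Week 12/Week 16 disagreement over the primary endpoint. Settling that disagreement either way does not bring Week 24 data forward to Week 16.

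**Working it through.** The plan gives no power, precision or accrual figure, so there is no figure of its own to reproduce. The check has three steps.

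**1. Count of efficacy results (Synopsis and Section 8.2)**

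| Measure | Week 12 | Week 24 |
|---|---|---|
| WI-NRS reduction of at least 4 | 1 (primary) | 1 |
| IGA PN-S 0 or 1 | 1 | 1 |
| IGA PN-A 0 or 1 | 1 | 1 |
| Percent improvement, PN-S | 1 | 1 |
| Percent improvement, PN-A | 1 | 1 |
| DLQI improvement | 1 | 1 |
| Total | 6 | 6 |

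So 6 of 12 are at Week 24. If the two percent-improvement measures count as one, it is 5 of 10. If the primary is read as Week 16, the split is 5 at Week 12, 1 at Week 16 and 6 at Week 24, and the Week 24 share is still half.

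**2. Subjects without Week 24 data at the cut-off**

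Inputs: N = 25 (Section 8.2); cut-off at Week 16 of the last subject (Section 8.2.1). Assumptions: enrolment evenly spaced over A weeks, and no dropout.

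- Subject i (i = 0 to 24) enrols at week A × i/24.
- The cut-off is at week A + 16.
- Week 24 is observed if A × i/24 + 24 ≤ A + 16, that is, if i ≤ 24 × (A − 8)/A.

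| A (weeks) | 24 × (A − 8)/A | Week 24 observed | Week 24 pending |
|---|---|---|---|
| 4 | negative | 0 | 25 |
| 8 | 0 | 1 | 24 |
| 13 | 9.2 | 10 | 15 |
| 26 | 16.6 | 17 | 8 |
| 52 | 20.3 | 21 | 4 |
| 104 | 22.2 | 23 | 2 |

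The number pending does not reach zero. With an analysis after all continuing subjects complete Week 24, it is 0 apart from dropouts.

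**3. What this does to precision**

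The plan names no interval method. As an illustration, I assume a response rate near one half and use exact (Clopper-Pearson) 95% intervals.

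| Responders / n | 95% interval | Width |
|---|---|---|
| 12/25 | 0.278 to 0.687 | 0.409 |
| 10/21 (A = 52) | 0.257 to 0.702 | 0.445 |
| 8/17 (A = 26) | 0.230 to 0.722 | 0.492 |
| 5/10 (A = 13) | 0.187 to 0.813 | 0.626 |

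The loss is modest with slow accrual and large with fast accrual.

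**The case against.** **A later analysis may be intended.** Calling this the Primary Analysis, and speaking of continuing subjects, leaves room for one. A reader might infer that Week 16 is the only analysis and that later data will be discarded. The documents do not support that: every subject is scheduled for assessment at Weeks 20 and 24, and an omitted sentence on the final analysis is the likelier explanation. What remains is that no later analysis is described anywhere, and the sentence still assigns the Week 24 endpoints to the Week 16 cut-off.

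**The no-imputation rule does not discard late enrolees.** This is fair. That rule concerns missing data and premature discontinuation, and a visit not yet due is neither. But a subject who has not reached Week 24 has no value to contribute under any rule.

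**Early knowledge of results.** A reader might also infer that an efficacy readout at Week 16 would bias later ratings or dose decisions, given "The investigator may reduce the dose to 15mg QD after week 16 per investigator discretion". The documents do not support that either. The study is open-label and single-arm at one centre, the site already sees every score, and nothing links dose changes to the pooled result.

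**Exploratory purpose.** No test, alpha or power is stated, so there is no error rate to inflate. This stands and limits the severity.

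**Conclusion.** The timing rule is wrong as written: half of the efficacy results (6 of 12) cannot be complete at the stated cut-off, and nothing in the document schedules their analysis. That count and the 8-week gap come directly from the text. The number of subjects affected does not. It rests on an assumed accrual period, even enrolment and no dropout, and runs from 2 to 25 of 25 over the accrual periods examined (104 down to 4 weeks).

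The primary endpoint is due by the cut-off on either reading of its week. Because the study is exploratory and single-arm, this is a point that should be fixed, not one that undermines the trial.

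**What to change.** Change the timing sentence in Section 8.2.1 in one of two ways:

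- **Single analysis:** analyse all efficacy endpoints after all subjects have completed Week 24 or left the study.
- **Two analyses:** limit the Week 16 analysis to endpoints due by that visit, and state that all Week 24 endpoints are analysed after the last subject's Week 24 visit.

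The second option keeps the Week 16 readout if the sponsor wants it.

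Two related items belong in the same edit. Review the deadline for per-protocol exclusions, now set before Week 16, against the new timing. Reconcile the week of the primary endpoint: the Synopsis says Week 12, Section 8.2 gives both Week 12 and Week 16, and Section 6 mentions Week 16.

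The cost is a short text change with no new visit or subject. The Week 24 readout comes up to 8 weeks later (24 − 16); under a single analysis, so does the readout of the other efficacy endpoints.

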## PROTOCOL SYNOPSIS

Study Title	A 24 Week, Open-Label Study to Evaluate the Efficacy and Safety of Upadacitinib in Patients with Moderate-to-Severe Prurigo Nodularis
Sponsors	[name]
Study Objectives	
Primary Objective: To explore the effectiveness of upadacitinib in patients with prurigo nodularis.
 
Secondary Objectives: To explore the safety of upadacitinib in patients with prurigo nodularis.

Study Design	A single center, open-label study of 25 subjects to assess 24 weeks upadacitinib in patients with moderate-to-severe prurigo nodularis.
Study Centers	Eczema Treatment Center of New Jersey [name]
Study Population	25 adult male and female subjects with moderate-to-severe prurigo nodularis
Main Inclusion Criteria	
 
1. Male or female adult 18-64 years of age at time of screening.
 
2. Diagnosis of prurigo nodularis for <math>\geq</math> 3 months.
 
3. Moderate-to-Severe prurigo nodularis as determined by at least 10 PN lesions on legs and/or arms and/or trunk at screening and baseline .
 
4. Failure of at least a 2-week course of medium to super potent TCS or TCS is not medically advisable for subject.
 
5. Females of childbearing potential must not have a positive serum pregnancy test at the Screening Visit and must have a negative urine pregnancy test at the Baseline Visit prior to study drug dosing. Note: subjects with borderline pregnancy test at Screening must have a serum pregnancy test <math>\geq</math> 3 days later to determine eligibility. If female, subject must be postmenopausal OR permanently surgically sterile OR for females of childbearing potential practicing at least one protocol specified method of birth control, that is effective from the Baseline Visit through at least 30 days after the last dose of study drug. Female subject must not be pregnant, breastfeeding or considering becoming pregnant during the study or for approximately 30 days after the last dose of the study drug.
 
6. Subject is a candidate for systemic therapy per investigator discretion.
 
7. Able and willing to give written informed consent prior to performance of any study-related procedures.
 
8. Subject must be in general good health as judged by the Investigator, based on medical history, physical examination.
 

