### **5.4 Subject Enrollment and Treatment Assignment**

25 adult subjects of either gender with moderate-to-severe prurigo nodularis will receive upadacitinib 15mg once daily. Dosage will be increased to 30mg QD at week 8 based on subject response. See dosage adjustments below. IP will be managed by site personnel and stored in a temperature controlled limited access area at the study site. Accountability records will be maintained by site personnel for all IP receipt, dispensation and returns.

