#### **Statistical Analyses for Efficacy**

All efficacy endpoints will be analyzed on the ITT population. In addition, the primary efficacy endpoints will be analyzed in the Per-Protocol Population, if defined.

No missing data imputation will be applied, and all assessments prior to premature discontinuation from study drug will be used.

Statistical Analyses for Safety – how will data be summarized? % of patients with AEs? The safety analyses will be carried out using the Safety Population. % of patients with AE's will be assessed inclusive of physical examination, laboratory assessments, and vital sign abnormalities.

Note that missing safety data will not be imputed.

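### ITT and Safety Populations are defined by a randomisation that never happens; the efficacy set needs a valid definition and a rule for subjects with no endpoint assessment

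*Combined protocol and SAP*

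**What the plan says.** The Synopsis describes "A single center, open-label study of 25 subjects to assess 24 weeks upadacitinib in patients with moderate-to-severe prurigo nodularis". Section 5.4 says that "25 adult subjects of either gender with moderate-to-severe prurigo nodularis will receive upadacitinib 15mg once daily", and Section 8.2 gives the size only as a target: "It is desired to enroll 25 patients". No section describes a comparator or a random allocation step.

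Section 8.2.1 nevertheless states: "The Intent-to-Treat (ITT) Population consists of all randomized subjects and will be used for the efficacy analyses". It continues: "The Safety Population consists of all randomized subjects who received at least 1 dose of study drug". The same section defines a third set, the All Upadacitinib Treated Population, by receipt of at least one dose without reference to randomisation, and assigns it to a comprehensive safety summary. A Per-Protocol Population is optional, and its criteria are deferred to a SAP that does not set them out here.

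The part headed Statistical Analyses for Efficacy ties the results to these sets: "All efficacy endpoints will be analyzed on the ITT population", and "The safety analyses will be carried out using the Safety Population". It also says that missing data will not be imputed and that assessments made before premature discontinuation of study drug will be used. It does not say whether a subject with no value at the endpoint visit remains in the denominator of a responder percentage.

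**The concern.** The term randomization also appears in exclusion criterion 9 (Section 5.2.2), where it decides no result. In Section 8.2.1 it is part of the definition that supplies the denominator of the primary endpoint, the proportion of participants with a WI-NRS reduction of at least 4. Because no one is randomised, that definition selects no one, and the optional Per-Protocol set is no fallback.

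A single-arm study has no control group against which a denominator effect could cancel. The responder percentage is the result, so a reader must know exactly who is in the denominator. Two questions need an answer: what replaces the word randomized, and what happens to a subject in the set who has no assessment at the endpoint visit. The second can matter more than the first.

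**Working it through.** **Inputs from the documents.** Target enrolment 25 (Section 8.2); one open-label group, all on upadacitinib (Synopsis, Sections 5.1 and 5.4); dosing from the baseline visit (Section 5.5.1.1); set definitions (Section 8.2.1); assignment of sets and no imputation (Statistical Analyses for Efficacy). The plan gives no expected response rate, dropout or power, so there is no figure of its own to reproduce.

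**Assumptions, for illustration only.** Responders r = 12 (range 10 to 15); enrolled but never dosed u = 0 to 3; dosed but without the endpoint assessment m = 0 to 5. The documents give none of these counts.

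**Step 1: size of each set as written.** Number randomised = 0. ITT = 0 and Safety = 0, so a percentage on either is 0/0 and undefined. All Upadacitinib Treated = number dosed, up to 25.

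**Step 2: replace randomized with enrolled.** ITT = 25. Safety = 25 − u. All Upadacitinib Treated = 25 − u. The two safety sets are identical for every u. With an assumed 5 subjects reporting an adverse event, both give 5/25 = 20.0% if u = 0, or 5/22 = 22.7% if u = 3. The two labels never give different answers.

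**Step 3: effect of the wording alone on efficacy.** Compare r/25 (enrolled) with r/(25 − u) (dosed), r = 12, everyone dosed being assessed:

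| Never dosed, u | Enrolled | Dosed | Difference |
|---|---|---|---|
| 0 | 12/25 = 48.0% | 12/25 = 48.0% | 0 |
| 1 | 48.0% | 12/24 = 50.0% | 2.0 points |
| 2 | 48.0% | 12/23 = 52.2% | 4.2 points |
| 3 | 48.0% | 12/22 = 54.5% | 6.5 points |

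Dosing begins at baseline and only eligible subjects are enrolled, so u should be zero or close to it. A set defined by dosing would also leave these subjects out, so a difference arising this way is not something that such a definition removes.

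**Step 4: effect of the silence on missing assessments.** Take u = 0 and r = 12, and compare r/25 with r/(25 − m):

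| Unassessed, m | All dosed counted | Observed cases | Difference |
|---|---|---|---|
| 2 | 48.0% | 12/23 = 52.2% | 4.2 points |
| 3 | 48.0% | 12/22 = 54.5% | 6.5 points |
| 4 | 48.0% | 12/21 = 57.1% | 9.1 points |
| 5 | 48.0% | 12/20 = 60.0% | 12.0 points |

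At m = 5 the difference is 10.0 points for r = 10 (10/25 = 40.0%, 10/20 = 50.0%) and 15.0 points for r = 15 (15/25 = 60.0%, 15/20 = 75.0%).

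**Step 5: precision, for scale.** The exact (Clopper-Pearson) 95% limits are the 2.5% quantile of Beta(x, n − x + 1) and the 97.5% quantile of Beta(x + 1, n − x). For 12/25 they are 27.8% and 68.7%, a width of 40.9 points; for 12/22 they are 32.2% and 75.6%. The differences in Step 4 lie within the sampling error, but dropping unassessed subjects can only raise the percentage for a given number of responders.

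**The case against.** The strongest reply is that this is leftover template language with an obvious meaning. Section 2.3 puts consent before enrolment, Sections 5.2.1 and 5.6.1 enrol only those who meet the criteria, Section 5.4 has all 25 receiving drug, and dosing starts at baseline. A set of all consented subjects is therefore not a plausible reading, and enrolled, eligible and dosed subjects should nearly coincide. The study is exploratory, and its statistical sections state no test or threshold that a small change could cross. All of this stands, and it is why the wording alone carries little weight.

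A reader might go further and infer that every efficacy and safety percentage has an open denominator. The documents do not support this for safety. The Safety Population also requires a dose, which fixes its membership once the stray word is corrected, and the All Upadacitinib Treated Population is well defined as written.

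A reader might also infer that the denominator would be chosen after responses are known. An open-label design makes responses visible, but nothing in the plan says the choice would wait for them. For the one set with discretionary exclusions, Section 8.2.1 requires these to be finalised before week 16.

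Finally, one could argue that an ITT label and an endpoint worded as a proportion of participants already imply that everyone is counted. That is a reasonable reading, but without imputation a subject with no value has no responder status, and the text does not say that such a subject counts as a failure. This part of the objection does not answer the concern.

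**Conclusion.** The point holds in a limited form. As written, the only set named for all efficacy endpoints has no members, and the definition should be corrected. For safety, the defect is two names for one set. Replacing the word should change the efficacy denominator little or not at all.

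What can change the reported result is the unstated treatment of subjects without the endpoint assessment: 6.5 points with three such subjects and 12.0 with five, given 12 responders among 25 dosed, and 10.0 to 15.0 points with five missing for 10 to 15 responders. These sizes rest on assumed counts and on enrolment reaching 25. They should not be attributed to the word randomized, which would produce the 6.5 points only if three enrolled subjects were never dosed.

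**What to change.** 1. In Section 8.2.1, replace the ITT and Safety definitions with a single Full Analysis/Safety Population: all enrolled subjects who received at least one dose of upadacitinib. Use that name under Statistical Analyses for Efficacy and for the safety analyses.
2. Delete the All Upadacitinib Treated Population, which duplicates it.
3. State that every responder percentage (WI-NRS reduction of at least 4, IGA PN-S 0 or 1, IGA PN-A 0 or 1) uses the full count of this population, and that a subject lacking the assessment counts as a non-responder.
4. Amend the no-imputation sentence to agree with item 3, and report the observed-case percentage, with its own denominator, as a supplementary result.

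No new data or procedures are needed. Items 1 and 2 are wording only. Items 3 and 4 set a missing-data rule, and the cost is that the responder rate may read lower than an observed-case figure, since a subject lost for reasons unrelated to treatment counts as a failure. The supplementary result lets the reader see how much of the difference is due to that rule.
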